## 7.7 Loss to follow-up

If after posting the questionnaires to the patient their return is not forthcoming, two reminder telephone calls should be made to them. If these calls prove unsuccessful, a reminder letter should be sent.

The timing of the reminder calls and letter is at the discretion of the treating hospital, however a suitable time-frame should be implemented and care should be taken in the timing of the final reminder letter so it allows sufficient time for the completion of the questionnaires within the stipulated +/- allowance for the post-op time point.

**IRAS Ref: 271885** Page 41 of 89

If no reply is received after the letter has been posted and sufficient time allowed for completion and return of the questionnaires, the patient shall be classed as lost to follow-up and the relevant CRF completed and provided to LCTC.

**IRAS Ref: 271885** Page 42 of 89

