#### Quantitative questions:

The most important of these is to determine whether it is possible to recruit an adequate number of patients within a suitable timeframe to the study. A number of recent national orthopaedic RCTs have suffered from low recruitment rates. It is

**IRAS Ref: 271885** Page 26 of 89

therefore important to identify realistic recruitment rates prior to engaging upon the full study.

The primary outcome measure for the full study will be a patient-reported functional outcomes questionnaire. In order to perform accurate sample size calculations, we need to know the variability (standard deviation) and loss to follow-up rate for the proposed method of collection of these scores.

One concern with comparative surgical trials is that during surgery, the surgeon may decide to use the alternative method due to some new or unforeseen intraoperative surgical finding. This would potentially skew the trial results and the rate of this occurrence is unknown. Whilst we will analyse the functional results on an intention to treat basis, we will measure the rate of treatment cross-over during surgery. During the feasibility study, the opportunity will also be used to survey potential sites and surgeons for their willingness to be involved in a future trial and to estimate the number of patients that may be included.

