## 7.5 6 weeks post-op

All patient participants will be reviewed in a routine outpatient clinic at 6 weeks postoperatively (from date of surgery). Please also see section 7.12 on contingency planning.

PROMS questionnaires to be completed are listed below. The Oxford Hip Score is to be completed first, others are shown in a recommended order of completion of most recent recall period:

- Oxford Hip Score
- EQ-5D-5L™
- Self-Administered Patient Satisfaction scale
- Forgotten Joint Score
- Work Productivity and Activity Impairment—Specific Health Problem

Data will also be collected Adverse Events of Special Interest; these will primarily be surgical complications, such as but not limited to returns to theatre for dislocation, fracture or wound problems; any prescriptions for antibiotics will be noted and any unanticipated contact with the surgical team or GP regarding the surgery.

The earliest this visit can occur is 3 weeks postop and the latest is 12 weeks postop from the date of surgery. Visits outside of these parameters will be recorded as protocol deviations but will not affect the patients continuing participation in the trial.

Every effort should be made to meet the patient in person during the visit. Should this not be possible the questionnaires should be posted as soon as possible to the patient for their completion. Details on how and when to return the questionnaires are included within the covering letter. (See also section 7.7 Loss to follow-up.)

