## 7.6 3-6 month post-op

Patient participants will be required to complete their PROMS questionnaires and healthcare resource use survey between 3 and 6 months postoperatively (from date of

**IRAS Ref: 271885** Page 40 of 89

surgery). This follow-up period will be dictated by the remaining duration of the study. All patient participation activity is expected to be completed by the end of October 20201. See the table below.

Month of Operation	Follow-up time point	Follow-up duration
January '21	July '21	6 months
February '21	August '21	6 months
March '21	September '21	6 months
April '21	October '21	6 months
May '21	October '21	5 months
June '21	October '21	4 months
July '21	October '21	3 months

PROMS questionnaires and a healthcare resource use survey will be sent in the post for the patient participant to complete. The accompanying cover letter will advise that the Oxford Hip Score is to be completed first, others are shown in a recommended order of completion of most recent recall period:

- Oxford Hip Score
- EQ-5D-5LTM
- Self-Administered Patient Satisfaction scale
- Forgotten Joint Score
- Work Productivity and Activity Impairment-Specific Health Problem
- Healthcare Resource Use Survey

A member of the hospital research team will contact the patient participants by phone before distribution to inform them of the upcoming postal questionnaires. The questionnaires should be posted early enough that the patient participant is in possession of them at the required 3-6 month post-operative date.

Patient participants will also be asked about any return to theatre required and any unanticipated contact with the surgical team or GP regarding the surgery.

The earliest that this data can be collected is 4 months postoperatively and the latest time is 8 months. Completion of these questionnaires outside of these parameters will be recorded as protocol deviations but will not affect the patients continuing participation in the trial.

Details on how and when to return the questionnaires are included within the covering letter.

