## 7.12 Contingency planning

In the event of national emergency (e.g. COVID-19) which prevents patients attending routine hospital appointments, the following amendments to practice will be followed:

- Any suspension of recruitment will be based on national guidance regarding elective surgeries, i.e. recruitment will be suspended temporarily if elective surgeries are postponed.
- If routine post-operative clinic appointments are postponed, PROMS for completion at 6-weeks post-op will be posted to the patients for their completion at home.

**IRAS Ref: 271885** Page 45 of 89

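### Section 7.7 records non-return of a posted 6-week questionnaire as loss of the patient while the 3-6 month assessment is still due, which could overstate loss to follow-up

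*Protocol*

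**What the plan says.** **The rule (Protocol 7.7).** When posted questionnaires are not returned, the site makes two reminder calls and then sends a letter. If there is still no reply, "the patient shall be classed as lost to follow-up and the relevant CRF completed and provided to LCTC". The reminders are to be timed so that completion falls "within the stipulated +/- allowance for the post-op time point". No particular time point is named.

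**The 6-week assessment (Protocol 7.5 and 7.12).** The normal route is an in-person clinic visit. "Should this not be possible the questionnaires should be posted as soon as possible to the patient for their completion". The same paragraph ends with a pointer: "See also section 7.7 Loss to follow-up". Under the national-emergency contingency in 7.12, if clinics are postponed, "PROMS for completion at 6-weeks post-op will be posted to the patients for their completion at home". On the window, 7.5 says: "The earliest this visit can occur is 3 weeks postop and the latest is 12 weeks postop from the date of surgery".

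**The final assessment (Protocol 7.6).** "PROMS questionnaires and a healthcare resource use survey will be sent in the post for the patient participant to complete". The nominal time is 3 to 6 months after surgery, depending on the month of operation.

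**What the rate is for (Protocol 2.2 and 11.2.2).** For the full trial's sample size, "we need to know the variability (standard deviation) and loss to follow-up rate for the proposed method of collection of these scores". Section 11.2.2 lists loss to follow-up as item 3(iv) without a time point. Trial withdrawal, by contrast, is to be reported at both 6 weeks and 3-6 months.

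**The concern.** The rule attaches to the patient, not to the assessment. Applied at 6 weeks, it turns one missed intermediate questionnaire into loss from the study while the last assessment has yet to take place. The usual meaning of loss to follow-up, and the one a sample size inflation needs, is absence at the time point on which the full trial will be analysed.

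Two things are at stake. The first is the recorded rate. A patient who misses the 6-week return but would answer at 3-6 months counts as lost, and no opposite error offsets this, so the rule can only push the rate up. That matters more than usual here, because the study exists to supply such rates: postal/telephone capture is a secondary objective (section 2.3) and retention is part of the feasibility judgement (section 11.5). The second is the final data. Once a loss-to-follow-up CRF has been filed, the protocol does not tell the site whether to send the 3-6 month pack.

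**Working it through.** The protocol states no expected loss-to-follow-up or dropout figure, so there is none to reproduce. The check is a reading of the text followed by an illustration.

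**Does the rule reach the 6-week time point?**
- Section 7.7 speaks of the questionnaires and the post-operative time point in general terms.
- Table B gives an allowance for both time points. At 6 weeks it is -3/+6 weeks, that is 6 - 3 = 3 and 6 + 6 = 12 weeks, which matches 7.5.
- The pointer to 7.7 stands in 7.5. Section 7.6 has no such pointer. A reading that confines 7.7 to the final mailing is therefore hard to sustain.

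**Is the final assessment still due when the rule bites?** The 6-week window closes at 12 weeks. The nominal final time point is then about 1 week away on the 3-month schedule (13 - 12) and about 14 weeks away on the 6-month schedule (26 - 12). So it is still to come, though for July operations the two nearly coincide.

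**Size per patient.** Let d be the true loss at the final time point and k the number who miss the posted 6-week return but would return the final pack. With 40 randomised (section 4.1):

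recorded loss = d + k/40

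Each such patient adds 1/40 = 2.5 percentage points. If k = 0, nothing is added.

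**Size under assumed return behaviour.** None of these rates is in the protocol.

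- *A quarter posted, 15% of those not returned, half of the non-returners answer later:* k = 40 × 0.25 × 0.15 × 0.5 = 0.75 of a patient; 0.75/40 = 1.9 points.
- *All 40 posted (7.12 in force), same 15% and half, with 10% final non-return among the other 34:* true loss = (3 + 3.4)/40 = 16.0%; recorded = (6 + 3.4)/40 = 23.5%; difference 7.5 points.
- *All 40 posted, 6-week non-return of 10%:* true (2 + 3.6)/40 = 14.0%; recorded (4 + 3.6)/40 = 19.0%.
- *All 40 posted, 6-week non-return of 20%:* true (4 + 3.2)/40 = 18.0%; recorded (8 + 3.2)/40 = 28.0%.

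**Effect on the full trial.** N = evaluable/(1 - loss), rounded up, taking 400 evaluable patients and d = 10% as illustrative assumptions:

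| k | Loss used | N | Change before rounding |
|---|---|---|---|
| 0 | 10% | 400/0.900 = 445 | none |
| 1 | 12.5% | 400/0.875 = 458 | +2.9% |
| 2 | 15% | 400/0.850 = 471 | +5.9% |
| 4 | 20% | 400/0.800 = 500 | +12.5% |

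For d between 5% and 20%, the increase is 2.7% to 3.2% at k = 1 and 11.8% to 14.3% at k = 4.

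**The case against.** **Nothing in the text ends follow-up.** Section 7.7 requires a classification and a form. Section 5.2 sets out how patients leave the study, and questionnaire non-return is not among the routes. Section 7.6 separately requires the final questionnaires, with a telephone call before they are posted. A reader might infer that a site would stop sending the final pack. The documents do not support that: they neither withhold the pack nor confirm that it is still sent. This part of the objection stands, and the loss of final data is only a possibility. Safety events are in any case also picked up through admissions and the patient card (section 12.7).

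**Other summaries exist.** Section 11.3 refers to the retention rate, section 10.5 to retention and return rates for the EQ-5D-5L and the resource-use survey, and section 11.2.2 to the proportion of missing data. A patient who answers at 3-6 months could be counted as retained from these, and an analysis plan could define item 3(iv) by time point. This stands as partial mitigation. It works only if the final data are still collected, and the wording in 7.7 is an instruction to sites that an analysis plan cannot undo afterwards.

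**The size may be small.** In-person contact is the preferred 6-week route, and posting everyone depends on the contingency. With 6 of 40 lost (15%), the Wilson 95% interval is about 7% to 29%, so a shift of about 2 points lies well within sampling error. This also stands. It limits how much the error matters but does not make the rule right.

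**No direct contradiction with 7.5 or 7.6.** A reader might infer that 7.7 conflicts with the statements there that missing a window leaves participation unaffected. Those statements concern visits or questionnaires completed outside the window, not questionnaires never returned, so there is no conflict.

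**Conclusion.** The point holds in conditional form. As written, 7.7 together with 7.5 records a missed posted 6-week return as loss of the patient before the final assessment is due, and this can only raise recorded loss relative to true final loss.

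It would be going too far to say that the rate is inflated. That requires sites to apply the rule at 6 weeks, at least one such patient who would have answered at the end, and use of the label for item 3(iv) or for sizing the full trial. Given those conditions, the error is 2.5 percentage points per patient with 40 randomised. The total is unknown: it may be zero, is about 2 points in the quarter-posted illustration, and is 5 to 10 points in the all-posted illustrations. All of these totals rest on assumed return rates. The defect is inexpensive to remove and worth correcting, because the affected rate is one that the study was set up to provide.

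**What to change.** In section 7.7:

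- State that non-return of the 6-week questionnaires after the reminders is recorded as a missed assessment, and that the patient stays in follow-up and receives the 3-6 month pack.
- Assign loss to follow-up only when the 3-6 month questionnaires are not returned after the reminders.

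Align the loss-to-follow-up CRF instruction with this, and report 6-week capture and final loss to follow-up as separate figures.

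The cost is a short text edit and a CRF instruction. No extra visits, staff or patients are needed.

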## 7.8 Schedule of trial procedures

Table B below describes Workstream 1 procedures and their time-points.

Table B: Trial procedures

able B. That procedures						
	TIMEPOINT					
PROCEDURE	Screening	Baseline	Randomisation	Day of surgery	Routine 6 weeks Post-op (-3 weeks / +6 weeks)	3-6 months Post-op (-2 month / +2 months^)
Identify eligible patient from records	Х				•	
Approach patient and discuss trial	Х					
Obtain Consent	Х					
Randomise patient			Х			
Demographics	Х					
PROMS – Oxford Hip Score		Х			Х	Х
PROMS – EQ-5D-5L TM		Х			Χ	X
PROMS – Self-Administered Patient Satisfaction Scale					X	X
PROMS – Forgotten Joint Score		Х			Х	Х
PROMS – Work Productivity and Activity Impairment–Specific Health Problem		Х			Х	Х
Healthcare Resource Use Survey		Х				Х
Data collection on routine surgery				Х		
Report Serious Adverse Events or Incidents				X	X	Х

^Yet no later than October 2021

**IRAS Ref: 271885** Page 43 of 89

## 7.9 Procedures for assessing Efficacy

Clinicians will use their usual criteria to determine if an intervention is deemed to have failed clinically and if a re-intervention is necessary. This information will be recorded in the patient participant's notes and on the appropriate CRF. The nature of any re-intervention will be at the discretion of the treating clinician who will use their skill, knowledge and expertise to determine the most appropriate treatment.

## 7.10 Procedures for Assessing Safety

Safety will be assessed through reporting on post-operative Adverse Events as described in section 12.

## 7.11 Quality of Life and Health Economics

Health Related Quality of Life and Health Economics outcomes measures

Health-related quality-of-life (HRQL) and other outcomes for use in the health
economics component of the study will be assessed using the following
questionnaires:

- Oxford Hip Score (OHS)
- EuroQol 5 Dimension, 5 Level Quality of Life Questionnaire (EQ-5D-5L™)
- Self-administered Patient Satisfaction scale (SAPS)
- Forgotten Joint Score (FJS)
- Work Productivity and Activity Impairment-Specific Health Problem (WPAI-SHP)
- Healthcare Resource Use Survey

Baseline data will be collected prior to the patient participant being randomised, with further collections at 6 weeks and 3-6 months post-operation. The only exclusions to this are the Health Resource Use Survey data, which is only collected at baseline and 3-6 months post-operation and SAPS data, which is not collected at baseline and will only be collected at 6 weeks and 3-6 months post-operation.

- The Oxford Hip Score© is used to assess joint-specific pain and functional limitations encountered by the patient participant in day-to-day activities over the preceding 4 weeks.
- EQ-5D-5L™ is a preference-based HRQL measure comprising five domains, each with five levels. HRQL scores can be attached to each of the possible 3125 health states it describes.
- Self-administered Patient Satisfaction scale is a tool to measure patient satisfaction with their operation, pain, and ability to do daily activities and recreational activities.
- The Forgotten Joint Score is a 12 question scale used to measure joint awareness. It has been extensively validated to assess outcomes after total hip arthroplasty.
- Work Productivity and Activity Impairment-Specific Health Problem records data on work time and productivity over the preceding 7 days.
- The Healthcare Resource Use Survey is a HipHOP specific questionnaire

**IRAS Ref: 271885** Page 44 of 89

## 7.12 Contingency planning

In the event of national emergency (e.g. COVID-19) which prevents patients attending routine hospital appointments, the following amendments to practice will be followed:

- Any suspension of recruitment will be based on national guidance regarding elective surgeries, i.e. recruitment will be suspended temporarily if elective surgeries are postponed.
- If routine post-operative clinic appointments are postponed, PROMS for completion at 6-weeks post-op will be posted to the patients for their completion at home.

**IRAS Ref: 271885** Page 45 of 89

## 8 TRIAL CLOSURE

#### 8.1.1 Closure to recruitment

Investigators will be informed when patient participant recruitment is to cease.

Trial enrolment may be stopped at a site when the total number of participants for the trial has been obtained.

The trial will close to recruitment once all Workstream 1 patient participants have been randomised and all Workstream 2 patient, surgeon and other health professional participants have completed their interviews. These closures may not necessarily occur simultaneously.

#### 8.1.2 Trial closure

The end of the trial is defined to be the date on which data for all participants are frozen and data entry privileges are withdrawn from the trial database. The trial may be closed prematurely by the Trial Steering Committee (TSC).

Site and closure activities will be centrally coordinated and conducted in accordance with LCTC processes regardless of whether the trial closes as planned or prematurely. This includes activities such as:

- End of Trial notification to REC
- Trial-related materials reconciled and returned/disposed of as appropriate
- All site data entered onto the study database, discrepancies raised and satisfactory responses received
- Quality Control checks of the Investigator Site Files, Pharmacy Files and Trial Master File as appropriate.

**IRAS Ref: 271885** Page 46 of 89

#### 9 BLINDING

To prevent bias in the completion of their answers to PROMS questionnaires, it is key that for the duration of their time on the study, i.e. until the 3-6 month post-operative PROMS questionnaires have been completed, a patient participant remains blinded to the type of implant they have received.

It is acknowledged that it is impossible to blind the surgeon, operation team and other healthcare professionals to the type of implant the patient participant received. Members of the research team being aware of the implant type will have no bearing on the outcomes of the study, however every effort must be made to ensure that patient participants remain blinded to the type of implant they received, at least until a patient has completed their 3-6 months post-operation PROMS questionnaires. These efforts must include, but are not limited to:

- Excluding members of the research team from correspondence that reveals the randomised allocation of the type of implant.
- Ensuring the patient is provided with and wears ear plugs during surgery.
   Alternatively, they can provide their own device and earphones to listen to music etc. instead (earphones do not have to be to any particular standard or specification, e.g. 'noise cancelling').
- Ensuring post-operative documentation that the patient or research team may have access to (e.g. discharge letter, physiotherapy referral) do not refer to the type of implant used.
- Marking/Annotating the operation notes to advise the reader to not disclose or allude to the type of implant used when in communication with the patient or research team.

If a patient participant does accidentally becomes unblinded to the type of implant they have received, the relevant CRF will need to be completed and returned to LCTC. Such occurrences will be recorded as protocol deviations but will not affect the patient continuing participation in the trial. Corrective and preventative actions must be undertaken locally to prevent similar events leading to unblinding to other patients.

If a member of the research team accidentally becomes unblinded to the type of implant patient receives, it does not have to be reported to LCTC. Corrective and preventative actions must however be undertaken locally to prevent the patient becoming aware, e.g. remove/reduce interaction between the member of the research team and the patient participant if possible.

**IRAS Ref: 271885** Page 47 of 89

## 10 HEALTH ECONOMICS

#### 10.1 Introduction

Economic evaluations alongside randomised control trials (RCTs) are important to inform the cost-effectiveness of the healthcare intervention being evaluated. The purpose of a feasibility study is to inform the design of a larger RCT, therefore the main focus of the health economic analysis will be to critique the performance of data collection methods used to identify and measure costs and outcomes required to conduct a full economic evaluation.

#### 10.2 Outcomes

The National Institute for Health and Care Excellence (NICE) recommends economic evaluations apply cost-utility analysis (CUA) to assess the costs and consequences of healthcare interventions. In a CUA, quality-adjusted life years (QALYs) are used as the primary outcome which capture the quality and quantity of life in a single measure. A QALY is calculated by multiplying the quality of life by the quantity of life. The quantity of life is measured using a count of the number of life years. Quality is measured using preference-weighted surveys such as the EuroQol 5 Dimensions 5 levels (EQ-5D-5LTM). The EQ-5D-5LTM provides a simple descriptive profile and a single index value for health status with an associated utility tariff. Utility values will be calculated for participants and will be used to estimate Quality Adjusted Life Years (QALYs) as a measure of health benefit. Total QALYs will be estimated as follows:

$$QALY = \Sigma[(U_i + U_i + 1)/2] \times (t_i + 1 - t_i)$$

Here, U = utility value and t = time between assessments. The time between assessments is the time from baseline data collection to follow-up, i.e. 3-6 months. Patients will be asked to complete the EQ-5D-5LTM survey at baseline and between three and six months follow-up.

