## 4 TRIAL DESIGN

# 4.1 Overall Design

HipHOP is a randomised feasibility study in preparation for a phase III, two arm, blinded, multi-centre, pragmatic randomised controlled trial comparing fully cemented and hybrid total hip arthroplasty in patients undergoing total hip arthroplasty.

This feasibility study will have both quantitative and qualitative elements, referred to as Workstream 1 and Workstream 2 respectively.

The Workstream 1 population is patients undergoing a primary total hip arthroplasty. Patient participants will be recruited from three sites and randomised to the two arms of the trial to receive either a fully cemented hip implant, or a hybrid hip implant. A total of 40 patient participants will be randomised on a 1:1 ratio. Recruitment will take approximately 6 months. Patient participants will be blinded to the type of hip prosthesis received. All possible efforts will be made for the patient participants to remain blinded until their 3-6 month post-operative PROMS are completed to ensure the integrity of the outcomes reporting. Staff collecting outcome data will also be blinded where possible (see section 9).

There are no exclusions to the *size* of socket used in the procedure. Deviation from the socket *type* that is selected at random is allowed, but only if it is established during surgery that the randomised socket type is unsuitable.

Comparison of the types of implant will be made using data collected using Patient Reported Outcome Measures. A healthcare resource use survey will also be provided to patients to complete. Data from this survey will be used to determine if a cost analysis will be possible in a larger phase III study.

Participants would have reached the end of their study involvement once their 3-6 month post-operative visit has been completed.

The Workstream 2 population is patients who both accepted or declined participation in Workstream 1, consultant orthopaedic surgeons and other health professionals.

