## 10.5 Analysis

A descriptive analysis of the costs and outcomes data will be completed focusing on the extent to which:

- 1. The EQ-5D-5L™ is able to adequately capture differences in health status before and after the hip replacement procedure and across both treatment arms of the study;
- 2. The resource use survey is able to record data necessary to enable a full cost-effectiveness analysis of the two hip interventions;
- 3. The follow-up periods specified are correct to capture changes in health status and healthcare resource use; and
- 4. There is a pattern or random missing data for both the EQ-5D-5LTM and resource-use survey to assess responses, sensitivity, and patterns within the missing data; particularly for resource-use surveys where missing data is a common issue.

Descriptive statistics will also report baseline patient characteristics, retention of participants and return rates for the EQ-5D-5L™ and healthcare resource use surveys. A within-trial analysis will also be conducted to estimate an indicative cost per QALY for each hip replacement intervention. The base-case analysis will use the NHS tariff for each hip replacement intervention. However, in the knowledge that the hip replacement procedures do not cost the same amount, a secondary analysis will be conducted to estimate an indicative cost per QALY using the differential costs for each hip replacement.

Given this is a feasibility study, it must be emphasised that the cost per QALY results from this analysis serve as an indication of the potential cost-effectiveness of the hip replacement procedures. The results will not provide definitive evidence on the cost-effectiveness of the interventions.

**IRAS Ref: 271885** Page 49 of 89

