## 11 STATISTICAL CONSIDERATIONS

#### 11.1 Method of Randomisation

Once consent has been obtained, participants shall be randomised on a 1:1 basis including the participating site as a stratification factor. Randomisation lists shall be produced by the trial statistician at the LCTC using randomly permuted blocks with separate lists created for each stratification factor. Lists shall be created using Stata (version 15 or above) using the add-on package 'ralloc'.

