## 11.5 Analysis Plan

Feasibility and overall recruitment rate will be assessed at the opened sites by calculating the total number of patient participants randomised per month and the ratio of successful recruitment to eligible patients approached. Furthermore, observed recruitment rates, by site and overall, will be summarised along with a 95% confidence interval.

**IRAS Ref: 271885** Page 51 of 89

Much of the analysis will be performed using summary statistics and graphics. No formal assessments of efficacy, cost or safety across treatment arms will be made. All presentations of the data will take the form of summary analysis and graphical representations. Continuous data shall be presented using measure of median (interquartile ranges), whereas categorical data shall be presented in terms of frequencies of counts and associated percentages.

Primary and secondary outcomes will be compared between the two arms using a chisquared or Fisher's exact test.

All analyses shall be carried out on an intention to treat basis, retaining all patient participants in their initially randomised groups irrespective of any protocol deviations. The exception to this is the analysis of safety data which shall be analysed on the safety set which is defined by the type of arthroplasty that patients receive.

Feasibility of the study will be measured on the ability of the study to meet the recruitment targets and Stop/go criteria are defined on this basis.

Following 6 months of active recruitment, a target of 40 patient participants is set. If recruitment is  $\geq$  80% of this target ( $\geq$ 32 patients) a future full study can be considered feasible. If the observed recruitment rate is between 50% and 80% of the target (20-31 patients) then a future full study could potentially go ahead only if satisfactory measures can be taken to improve recruitment. Such measures must be realistic and have support of the study sponsor. If recruitment is less than 50% of the anticipated rate ( $\leq$ 19 patients) than the study won't be considered feasible to evolve into a full one in the future.

In addition, in order for the study to be considered feasible, it should not demonstrate any serious issues related to randomisation process, patient participant retention and/or protocol deviations.

Statistical analyses will be performed using a suitable recognised statistical software such as Stata v15 or above, R v3.3.0 or above and SAS v9.3 or above.

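### Indicative cost per QALY: sections 10.2 and 10.5 state no adjustment for baseline EQ-5D-5L utility, a low-severity gap that one regression on data already collected would close

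*Protocol*

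**What the plan says.** - **QALY definition (10.2).** "Total QALYs will be estimated as follows", followed by a trapezoid sum over successive utilities. On timing: "The time between assessments is the time from baseline data collection to follow-up, i.e. 3-6 months". The section names only the baseline and the 3 to 6 month EQ-5D-5L.
- **Data collected (7.11).** Baseline EQ-5D-5L is taken before randomisation, with "further collections at 6 weeks and 3-6 months post-operation".
- **Use (10.5).** "A within-trial analysis will also be conducted to estimate an indicative cost per QALY for each hip replacement intervention". The base case uses the NHS tariff, and section 10.3 says both procedures fall under the same tariff.
- **Status (10.5, 11.5).** Section 10.5 says "The results will not provide definitive evidence on the" cost-effectiveness of the interventions. Section 11.5 says "No formal assessments of efficacy, cost or safety across treatment arms will be made".
- **Size and balance (4.1, 11.1).** "A total of 40 patient participants will be randomised on a 1:1 ratio"; "participants shall be randomised on a 1:1 basis including the participating site as a stratification factor". Nothing else is balanced by design.
- **Follow-up length (7.6).** The table gives 6 months to patients operated on from January to April 2021, then 5, 4 and 3 months for May, June and July.

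The protocol contains no statement that QALYs will be adjusted for baseline utility, and none that rules it out.

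**The concern.** Baseline utility is part of each patient's QALY, so an arm that starts worse by chance is credited with fewer QALYs for a reason unrelated to the implant. Later utilities correlated with baseline carry some of the same imbalance.

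This matters a little more here because the base case puts both implants on one tariff. The procedure cost is then the same in each arm, so any difference between the two base-case figures comes from other resource use or from the QALY denominator. Section 10.5 presents these figures as a pointer to potential cost-effectiveness, and two per-implant figures side by side invite comparison. At stake are the precision of those figures and how they will be read.

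**Working it through.** **The plan's own figures.** The protocol gives no QALY, utility SD or implant effect to reproduce. The only figure attached to the 40 patients is the recruitment rate, 40/(3 × 6) = 2.22 per site per month, which agrees with section 11.3.

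**Inputs.** From the protocol: 20 per arm (4.1), and follow-up T of 0.25 to 0.5 years (10.2, 7.6). Assumed: utility SD 0.20 to 0.30, the same at each visit; baseline/follow-up correlation ρ of 0.2 to 0.6.

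**Step 1: chance baseline gap.** SE = SD × √(2/20).
- SD 0.20: 0.0632
- SD 0.30: 0.0949

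**Step 2: two-point QALY (baseline and final visit, as 10.2 is worded).** QALY = T × (U₀ + U₁)/2, so baseline has weight T/2, half of the total.
- T = 0.5: 0.25 × 0.0632 = 0.0158; 0.25 × 0.0949 = 0.0237
- T = 0.25: 0.125 × 0.0632 = 0.0079; 0.125 × 0.0949 = 0.0119

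For scale, an illustrative final-visit advantage of 0.05 would be worth 0.05 × 0.25 = 0.0125 QALY at 6 months. More generally, baseline and final visit carry equal weight here. A one-SE baseline gap therefore counts directly for as much as a final-visit implant effect of 0.063 to 0.095.

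**Step 3: three-point QALY (adding the 6-week EQ-5D-5L).** Baseline weight becomes (6/52)/2 = 0.0577 whatever T is. That is 0.0577/0.25 = 23% of the total at 3 months and 0.0577/0.5 = 12% at 6 months.
- 0.0577 × 0.0632 = 0.0036; 0.0577 × 0.0949 = 0.0055

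This is the direct effect only; the part carried by correlated later utilities is extra.

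**Step 4: what adjustment gains (two-point).**
- Unadjusted SE of the QALY difference: (T/2) × SD × √(2 + 2ρ) × √(2/n)
- Adjusted for baseline: (T/2) × SD × √(1 − ρ²) × √(2/n)
- Ratio: √((1 − ρ)/2) = 0.63, 0.55 and 0.45 at ρ = 0.2, 0.4 and 0.6

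Example with SD 0.25, ρ 0.4, T 0.5: 0.0331 unadjusted and 0.0181 adjusted, so 95% half-widths of 0.065 and 0.036 QALY.

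**Step 5: what adjustment does not fix.** Expressed as a final-visit utility difference, the adjusted half-width is 1.96 × SD × √(1 − ρ²) × √(2/20). This runs from 0.10 (SD 0.20, ρ 0.6) to 0.18 (SD 0.30, ρ 0.2), so the contrast stays imprecise.

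Unequal follow-up is a separate source of noise. Taking the seven months of the 7.6 table as equally likely, T has an SD of 1.125 months, or 0.0937 years. At an assumed mean utility of 0.6 the SE between arms is 0.6 × 0.0937 × √(2/20) = 0.018 QALY. The direct baseline term at SD 0.25 and T = 0.5 is 0.25 × 0.25 × √(2/20) = 0.020, so the two are of similar size. The baseline weight T/2 itself varies from 0.125 to 0.25 between patients, so a single baseline coefficient cannot remove the imbalance exactly.

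**The case against.** The strongest reply is that section 10.2 defines a patient's QALY and does not say how arm means will be estimated. The proposed regression keeps that QALY as its outcome. Covariates are commonly left to an analysis plan, and section 11.5 announces one that is not shown. It is therefore right that non-adjustment is inferred from silence. Two things remain. Section 10 goes as far as stating the estimator and its use. The announced plan is tied to the details in section 11, whereas health economics is assigned to a different university (1.6) and no separate economic plan is mentioned.

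The second reply is that nothing depends on the result: section 10.1 makes data collection methods the main focus, no incremental ratio is named, and progression in 11.5 rests on recruitment, randomisation, retention and deviations. This stands in full and sets the severity. Section 10.5 also reports baseline characteristics, so a reader could see an imbalance, although the cost per QALY would not be corrected for it.

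A reader might infer that chance imbalance would swamp any implant effect. The documents do not support this. They give neither an implant effect nor a utility SD, so the comparison rests on assumed values, and the direct effect is much smaller if the 6-week data are used. Nor should a reader infer that adjustment makes the comparison informative; Step 5 of the working shows it does not.

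**Conclusion.** The point holds as a low-severity improvement. The protocol states a raw area-under-the-curve QALY and a descriptive cost per QALY per implant, with no baseline adjustment, in a study small enough for chance gaps to matter.

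Under an assumed SD of 0.20 to 0.30, the shift per standard error of imbalance under the two-point reading is comparable to the effect of a modest utility advantage at the final visit. Adjustment would cut the standard error to about 45 to 63% of its unadjusted value, given ρ of 0.2 to 0.6 and equal SDs at the two visits.

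The effect is on the precision and readability of the indicative figures. The feasibility conclusion and the stop/go decision are untouched, and no planned inference is invalidated.

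**What to change.** Add to section 10.5 that mean QALYs per implant are estimated from a regression of QALY on randomised implant, baseline EQ-5D-5L utility and site. Because follow-up runs from 3 to 6 months, either put QALYs on a common horizon first or include follow-up duration as a covariate. Predict both implant means at the common covariate means, report them descriptively with the unadjusted means alongside, and use them in the indicative cost per QALY. State in 10.2 whether the 6-week EQ-5D-5L enters the sum, since this sets the baseline weight.

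The cost is a few lines of text and one regression, with no new data. With three sites the model has at most six parameters (intercept, implant, baseline, two for site, one for duration), leaving 40 − 6 = 34 residual degrees of freedom with complete data. Adjusted means remain descriptive, so they do not conflict with section 11.5, and they would try out the estimator for the cost-utility feasibility objective in section 2.3.
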